#### 4.1.1. *Current Standard of Care Therapy for WM*

Current recommendations are that asymptomatic patients with WM are observed and that treatment should not be based on IgM levels alone. Treatment should be initiated in response to the clinical complications noted above [6,8]. Selection of therapeutic agents may be tailored to the disease manifestations. The most common first-line regimens are combinations including the following agents:

- Rituximab (anti-CD20 monoclonal antibody).
- Cyclophosphamide or chlorambucil (alkylating agents).
- Doxorubicin (anthracycline antibiotic).
- Vincristine (alkaloid).
- Prednisone (corticosteroid).
- Fludarabine or cladribine (nucleoside analogs).

Ibrutinib has recently received Food and Drug Administration approval for the treatment of WM on the basis of a response rate of 61.9% (including complete response [CR], very good partial response [VGPR], and partial response [PR]) in a Phase 2 study of 63 patients.

Plasmapheresis is used for symptomatic hyperviscosity and other complications of high serum levels of monoclonal IgM protein.

Salvage therapy for patients with refractory or relapsing disease is diverse and use of investigational agents is often considered appropriate. Approaches in current practice include (a) alternative combinations of the agents noted above, with the possible addition of bortezomib or thalidomide, and (b) transplantation with autologous stem cells or allogenic bone marrow [6,7].

Many of the agents used in refractory or relapsing WM are cytotoxic or sharply immunosuppressive and have substantial safety risks in elderly patients characteristic of this disease. A novel targeted agent that provided a beneficial treatment effect with a better tolerability profile would address an unmet need in WM.

[figure not shown]
#### 4.2. Role of Toll-like Receptors (TLRs) in B-cell Malignancy

Toll-like receptors are a family of host sensors for “foreign” constituents (e.g., nucleic acids, lipopolysaccharides, peptidoglycans from viruses, bacteria, fungi) that “sound the alarm” and activate host immune defenses. The natural ligands for TLR7 and 8 are single-stranded ribonucleic acid (RNA) from viruses, and for TLR9, unmethylated cytosine-guanine dinucleotide motifs (CpG), which are characteristic of bacterial deoxyribonucleic acid (DNA). Binding of these ligands to the cognate receptor results in intracellular signaling, generation of nuclear factor kappa-light-chain-enhancer of activated B cells (NF- $\kappa$ B), and production of pro-inflammatory (Th1) chemokines and cytokines, including interferon (IFN)- $\alpha$ , tumor necrosis factor (TNF)- $\alpha$  and interleukin (IL)-12. Of note, TLRs 7, 8, and 9 are located in the endosome, whereas most other TLRs, which are located on the host cell surface. In man, the endosomal TLRs are expressed primarily on dendritic cells and B-cells.

Although foreign constituents are the intended ligands for the nucleic acid TLRs, multiple studies indicate that activation by endogenous nucleic acids is central to the development and persistence of autoimmunity and inflammatory diseases. [9,10,11,12,13].

The TLR signaling pathway (Figure-1, left panel) comprises a series of cytoplasmic proteins that result in generation of NF- $\kappa$ B, which translocates to the nucleus and mediates increased expression of genes involved in cell survival, proliferation, and cytokine production. In B-cells, the other major mechanism for activation is binding of specific antigen to the B-cell receptor (BCR). There are several signaling pathways associated with the BCR (Figure-1, right panel), including one that generates increased NF- $\kappa$ B. The constituents of that BCR signaling pathway are, in general, distinct from those of the TLR pathway.

**Figure-1. TLR and BCR Signaling Pathways in B-cells**

A central feature of malignant cell transformation is the development of dysregulated or autonomous cell activation resulting in increased cell proliferation and survival. This can be the result of specific ‘oncogene’ mutations or defects in the control of the expression of critical genes. Studies of B-cell malignancies have identified changes in the BCR signaling pathway, and more recently in the TLR signaling pathway, that drive NF-κB expression and the malignant phenotype. These changes include:

- Mutations in BCR pathway genes, including CD79A/B and CARD11 [3].
- Increased expression of myeloid differentiation primary response gene (88) (MyD88), the adapter (linker) protein that binds to TLRs [14].
- Mutations in MyD88 [15].

The most common alteration identified to date in MyD88 is the L265P mutation. Table-6 displays the frequency of MyD88 L265P among B-cell malignancies and proliferative diseases. The mutation is present in over 90% of WM, in ~30% of Activated B-cell-like Diffuse Large B-cell Lymphoma, and at lower frequencies in other, more common lymphomas.

**Table-6. Incidence of MyD88 L265P mutation in selected B-cell malignancies**

Disease	Incidence of Disease (SEER 2001)	% Patients with MYD88 L265P mutation	Estimated Incidence 2013 a (New cases/year)	Reference for MyD88 frequency
ABC-DLBCL	6,789 b	29%	2,150	[16]
Waldenström's macroglobulinemia	1,144	91%	1,200	[2]
Chronic Lymphocytic Leukemia	16,984	3%, 7%	925	[17,18]
Primary CNS Lymphoma	1,200	36%, 38%	480	[19,20]
Marginal Zone Lymphoma c	3,247	9%, 4%	225	[16,21]

Abbreviations: ABC-DLBCL=Activated B-cell (type) Diffuse Large B-cell Lymphoma; CNS=central nervous system; DLBCL=Diffuse Large B-cell Lymphoma; MyD88=Myeloid differentiation primary response gene (88); SEER=Surveillance Epidemiology and End Results

a. New cases/year are adjusted + 10% due to population growth since data collection [22,23]

b. Incidence of DLBCL, 24,246; ABC-type represents 28% of all DLBCL.

c. Marginal Zone Lymphoma is also referred to as MALT, Mucosa-Associated Lymphoid Tissue Lymphoma

Recent in vitro studies of B-cell tumor lines with L265P mutation suggest that increased TLR signaling contributes to the malignant phenotype of these cells [4]. Specifically, cell proliferation and survival decreased markedly under the following conditions:

- Impaired expression of endosomal TLRs, using an inhibitory RNA.
- Enzymatic elimination of endogenous nucleic acids in the culture supernatant.

Idera Pharmaceuticals, Inc. has conducted independent studies using B-cell tumor lines, including LY10, a cell line with the L265P mutation and increased MyD88 expression. LY10 cells cultured in vitro with IMO-8400 demonstrated decreased growth and survival (see Investigator Brochure for details). Severe combined immunodeficient mice inoculated with LY10 developed progressive disease and died. Treatment with IMO-8400 prolonged median survival from 33 to 48 days (see Investigator's Brochure for details).

Taken together, these data directly support the hypothesis that an antagonist of TLR7, 8, and 9 would have a therapeutic effect in patients with B-cell malignancies, particularly those characterized by MyD88 L265P mutation or increased MyD88 expression.

#### 4.3. Rationale for the Current Study

IMO-8400 is a synthetic oligonucleotide that blocks activation mediated through TLR7, 8 and 9; that is, it functions as an antagonist for those receptors.

To date, IMO-8400 in doses up to 0.6 mg/kg once weekly has been administered for 4 weeks in healthy volunteers and for 12 weeks in a completed Phase 2 psoriasis study (see [Section 4.4](#) for details). All treatments were well-tolerated, with mild injection site reactions and no pattern of systemic reactions or laboratory changes.

As detailed above, recent studies indicate a role for TLR activation and subsequent signal amplification by MyD88 L265P mutation in the activation, proliferation, and increased survival of malignant B-cells.

The current protocol represents the first use of IMO-8400 in patients with a B-cell malignancy.

#### 4.4. Overview of IMO-8400

IMO-8400 has been created by Idera Pharmaceuticals, Inc. using a structure-activity approach to design TLR-targeted drug candidates. IMO-8400 is a synthetic oligonucleotide designed to inhibit immune responses mediated through endosomal TLR7, TLR8, and TLR9.

Non-clinical studies (reviewed in detail in the Investigator's Brochure) have demonstrated that IMO-8400 is an immunomodulatory agent with the following characteristics:

- Acts as an antagonist for activation of TLR7, 8 and 9, specifically blocking the activity of agonists for those receptors, including inhibiting generation of NF- $\kappa$ B and induction of cytokines and chemokines (e.g., TNF- $\alpha$ , IL-12, IL-1 $\beta$ , IFN-inducible protein-10 [IP-10], IL-6, IFN- $\alpha$ ).
- Has no agonist activity; that is, does not induce Th1 cytokines/chemokines.
- Is specific for endosomal TLRs 7, 8, and 9; that is, has no effect on activation of other unrelated TLRs, such as TLR4, whose natural ligand is bacterial lipopolysaccharide.
- Has potent therapeutic activity in animal models of autoimmune diseases to inhibit the progression or reverse the clinical and immunologic manifestations of disease.

Further, Idera has recently completed laboratory studies both in vitro and in mice examining the effect of IMO-8400 on human lymphoma B-cell lines, including cell lines with and without mutations in the TLR signaling pathway. These studies demonstrate that IMO-8400 has the following effects:

- Inhibits constitutively active cell signaling pathways, including NF- $\kappa$ B, IRAK, STAT-3, Jak/Stat, and BTK, in human lymphoma cell lines with the MYD88 L265P mutation.
- Decreases in vitro cell survival and proliferation in a time- and concentration-dependent manner in human lymphoma cell lines with the MYD88 L265P mutation.
- Decreases tumor cell growth in vivo, as indicated by decreased serum levels of tumor-secreted cytokine, and increased mouse survival time in a disseminated xenograft model using OCI-Ly10, a human lymphoma cell line with the MYD88 L265P mutation.
- Decreases tumor growth and serum levels of tumor-secreted IL-10 in a subcutaneous (SC) xenograft mouse model using OCI-Ly10, a human lymphoma cell line with the MYD88 L265P mutation.
- Does not impact tumor growth and tumor-secreted cytokines in a SC xenograft mouse model using SU-DHL-6, a human lymphoma cell line with wild-type MYD88.

Clinical studies with IMO-8400 are summarized in [Table-7](#) and the IB. Clinical experience with IMO-8400 related to the rationale for the dosing regimen in the current study is provided in [Section 6.10.2](#).

**Table-7. Clinical Studies with IMO-8400 in Addition to This Study**

Protocol No.	Protocol Title	Status
8400-001	A Phase 1, Single-Dose Escalation and 4-week Multiple-Dose Escalation Study of the Safety and Pharmacokinetics of IMO-8400 in Healthy Volunteers	Completed
8400-201	A Randomized, Double-Blind, Placebo-Controlled, 12-week Dose-Ranging Trial of IMO-8400 in Patients with Moderate to Severe Plaque Psoriasis	Completed
8400-402	Phase 1/2 Open-label, Multiple-dose, Dose-escalation Study to Evaluate the Safety and Tolerability of IMO-8400 in Patients with Relapsed or Refractory Diffuse Large B-cell Lymphoma and Presence of the MyD88 L265P Mutation	Ongoing
8400-404	An Extension Study to Evaluate the Long-Term Safety, Tolerability, and Clinical Activity of IMO-8400 in Patients with Relapsed or Refractory Waldenström's Macroglobulinemia who Completed Study 8400-401	Ongoing
8400-211	A Phase 2, Randomized, Double-Blind, Placebo-Controlled Trial of IMO-8400 in Patients with Dermatomyositis	Ongoing

Abbreviations: MyD88=Myeloid differentiation primary response gene (88)

#### **4.4.2. Benefit/Risk Aspects**

The starting dose level for the present study (0.6 mg/kg once weekly by SC injection) has been well tolerated for up to 4 weeks in healthy volunteers and up to 12 weeks in patients with moderate to severe psoriasis. The majority of treatment-emergent adverse events (TEAEs) are mild injection site reactions; there were no treatment-related serious adverse events (SAEs) or discontinuations due to AEs. This starting dose is, therefore, considered to represent minimal risk.

In the context that patients enrolled in this study have no therapeutic options likely to extend their survival, the clinical and safety profile demonstrated thus far with IMO-8400 justifies their inclusion and their treatment until progression.

## 5. STUDY OBJECTIVES

### 5.1. Primary Objective

- To evaluate the safety and tolerability of escalating dose levels of IMO-8400 administered by SC injection in patients with relapsed or refractory WM.

### 5.2. Secondary Objectives

- To assess the treatment effect (clinical activity) of escalating dose levels of IMO-8400 using disease-specific international guidelines for classifying clinical response [1].
- To identify an optimal dose of IMO-8400 for further clinical evaluation.
- To characterize the pharmacokinetics (PK) of escalating dose levels of IMO-8400 administered by SC injection.

### 5.3. Exploratory Objectives

- To investigate associations between the treatment effect of IMO-8400 and selected biomarkers (e.g., serum cytokines).
- To correlate the presence of MyD88 L265P mutation with clinical outcome.
- To assess the potential immunogenicity of IMO-8400 administered by SC injection.

## 6. INVESTIGATIONAL PLAN

### 6.1. Overall Study Design

This is an open-label, multiple-dose, dose escalation study of IMO-8400 in patients with relapsed or refractory WM.

### 6.2. Dose-escalation Cohorts

The dose escalation cohorts (3 to 6 patients each) will systematically evaluate the safety and tolerability of IMO-8400 at increasing dose levels in order to identify the MTD/recommended Phase 2 dose (RP2D).

- The planned dose escalation cohort levels for IMO-8400 are 0.6, 1.2, 2.4, and 3.6 mg/kg administered once weekly and 1.2 mg/kg administered twice weekly ([Table-8](#)). Additional dose levels, schedules, and routes of administration may be evaluated based upon the emerging data. Weekly exposure is based on body weight (see [Section 8.1](#) for details). Doses will be administered by SC injection.
- For Dose Level 3 (refer to [Table-8](#)), the total dose will be divided into 2 equal portions (1.2 mg/kg twice weekly), administered as separate SC injections over the course of the week, preferably 72 to 96 hours apart (minimum 48 hours) (see [Section 8.4](#) for details).
- Once safety has been established for the 2.4 mg/kg/week as a divided weekly dose (1.2 mg/kg twice weekly), the same dose level of 2.4 mg/kg/week and subsequent dose levels will be given as a once weekly administration.
- Once the RP2D/MTD has been established, patients being treated at lower dose levels may have their doses escalated to the RP2D/MTD upon discussion and agreement between the Sponsor and the Investigator.

**Table-8. Planned Dose Escalation Cohorts**

Dose Level	IMO-8400 Dose (mg/kg)	Frequency	Initial Cohort Size
1 (starting dose)	0.6	Once Weekly	3-6
2	1.2	Once Weekly	3-6
3	1.2	Twice Weekly	3-6
4	2.4	Once Weekly	3-6
5	3.6	Once Weekly	3-6

## 6.3. Dose-escalation Procedures

### 6.3.1. ***Definition of a Dose-Limiting Toxicity and Dose Modifying Event***

The safety and tolerability of IMO-8400 will be assessed using reported and observed AEs as well as scheduled safety observations including vital signs, physical examination, laboratory tests (hematology, chemistry, and coagulation), urinalysis, and electrocardiograms (ECGs).

A DLT can be either a clinical or laboratory AE.

A potential DLT event is defined as a treatment-emergent AE (see [Section 10.1](#)) which occurs within the first 5 weeks of treatment and meets *any* of the following criteria using NCI CTCAE grading (see [Section 10.4.4](#)):

- Is a clinical event of Grade 3 or higher severity, except for the following:
  - Alopecia
  - Grade 3 fatigue
  - Grade 3 nausea/vomiting that has not been treated with optimal anti-emetic treatments
  - Grade 3 diarrhea that has not been treated with optimal anti-diarrheal treatments
  - AE related to the underlying disease
- Is a confirmed laboratory finding of Grade 3 or higher severity (see [Section 10.4.5](#)) and has been assessed as related to IMO-8400 (any relationship other than “not related”) with the exceptions of neutropenia and thrombocytopenia. DLTs with respect to neutropenia/thrombocytopenia are outlined below:
  - Grade 4 neutropenia lasting > 7 days
  - Grade 3 or 4 neutropenia with a sustained temperature > 101.3° F
  - Grade 3 thrombocytopenia associated with clinically significant bleeding that requires transfusion therapy
  - Grade 4 thrombocytopenia

Clinically significant toxicities or TEAEs that meet the definition of dose-limiting but occurring after Week 5 of Cycle 1 are defined as dose modifying events (DMEs) and may be considered when determining the RP2D.

The Data Review Committee (DRC) is comprised of the Idera Medical Monitor and Investigators from participating sites. The DRC will review all potential DLT events to assess causality, i.e., relationship to study drug (see [Section 10.4.3](#)). Events will be considered DLT events unless they are unanimously assessed as “Not related,” that is, a factor other than study drug is the cause of the event (see [Section 10.4.3](#)).

The definition of a DLT event will be applicable in the following contexts:

- DRC review determining dose escalation (see below).
- DRC review in defining the MTD (see below) or RP2D.

- Investigator (and Medical Monitor) review for determining pausing or discontinuation of study treatment in individual patients (see [Section 6.5](#)).

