#### **1.3.5. Dose-escalation Enrollment and Review**

Each dose-escalation cohort is expected to enroll at least 3 patients, with a maximum of 6.

- If the initial 3 patients all complete 4 weeks of treatment without a DLT event, the DRC will conduct a dose-escalation review.
- If 1 of the initial 3 patients experiences a DLT event prior to completing 4 weeks of treatment, then enrollment at that dose level will continue to a total of 6 patients and the dose-escalation review will be done when all 6 patients have completed 4 weeks treatment.
- If 2 patients at a dose-level experience DLT events during the first 4 weeks of treatment, then no further patients will be enrolled until the DRC completes a review, which should be done as soon as feasible.

The DRC review will include all safety data available for the cohort. The following represent anticipated outcomes for the review process.

- Dose escalation – progression to the next planned dose level.

- Continue cohort enrollment (applicable only to review after 3 patients) – enroll up to 6 patients at the current dose level to obtain additional safety data for subsequent review.
- Dose de-escalation – enrollment of intermediate dose levels for exploration of other schedules of administration (see [Section 6.5.2](#)).
- Approve enrollment in an expansion cohort at a selected dose level, if applicable (see [Section 1.3.6](#)).
- No further dose escalation enrollment – at this time the DRC will indicate the dose level that they consider represents the MTD.

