### **6.3.2. *Definition of Maximum Tolerated Dose and Recommended Phase 2 Dose***

The MTD is the highest dose level meeting *both* of the following criteria:

- It is below the level at which 2 or more patients experienced DLTs during the first 4 weeks of treatment;
- It is a dose level at which no more than 1 patient experienced DLTs during the first 4 weeks of treatment.

The RP2D will be a dose at or below the MTD based on clinical data.

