### **6.3.3. *Dose-escalation Enrollment and Review***

Each dose-escalation cohort is expected to enroll at least 3 patients, with a maximum of 6.

- If the initial 3 patients all complete 4 weeks of treatment without a DLT event, the DRC will conduct a dose-escalation review.
- If 1 of the initial 3 patients experiences a DLT event prior to completing 4 weeks of treatment, then enrollment at that dose level will continue to a total of 6 patients and the dose-escalation review will be done when all 6 patients have completed 4 weeks treatment.
- If 2 patients at a dose level experience DLT events during the first 4 weeks of treatment, then no further patients will be enrolled until the DRC completes a review, which should be done as soon as feasible.

Once the last patient in a given cohort has a completed 4 weeks of study treatment, a DRC meeting will be convened to review all safety data and to decide whether to continue or halt dose escalation, or explore intermediate dose levels. To facilitate standardizing the dose-escalation reviews across different cohorts, the focus will be on observations from the first 4 weeks of treatment at that dose level.

The following represent anticipated outcomes for the review process (refer to DRC Charter for full details):

- Dose escalation – progression to the next planned dose level.
- Continue cohort enrollment (applicable only to review after 3 patients) – enroll up to 6 patients at the current dose level to obtain additional safety data for subsequent review.
- Dose de-escalation – enrollment of intermediate dose levels for exploration of other schedules of administration (see [Section 6.5.2](#)).
- Approve enrollment in an expansion cohort at a selected dose level, if applicable (see [Section 6.4](#)).
- No further dose escalation enrollment – at this time the DRC will indicate the dose level that they consider represents the MTD.

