### **6.6. *Criteria for Replacement Patients***

#### **6.6.1. *Definition of a Evaluable Patient***

A patient will be considered evaluable for purposes of DRC review if they meet *either* of the following criteria:

- Received at least 1 dose of study drug and had treatment discontinued because of a DLT event as defined in [Section 6.3.1](#); or
- Received all doses of study drug in the first 4 weeks of treatment and completed Week 5 assessment procedures.

See [Section 12](#) for additional discussion of analysis for safety and efficacy.

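### A DLT is defined over 5 weeks but counted over 4 for escalation and the MTD, so the protocol does not settle whether a DLT on Days 29-35 counts

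*Protocol*

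**What the plan says.** Two windows appear in the dose-escalation rules.

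- **Five weeks.** Section 6.3.1 defines a potential DLT as a treatment-emergent event "which occurs within the first 5 weeks of treatment and meets" the listed criteria. Events that would be dose-limiting but arise after Week 5 of Cycle 1 become DMEs. The section lists where the definition applies, including the DRC's escalation review and "DRC review in defining the MTD (see below) or RP2D".
- **Four weeks.** The second MTD criterion in 6.3.2 reads "It is a dose level at which no more than 1 patient experienced DLTs during the first 4 weeks of treatment", and the first criterion uses the same period. The enrolment and review triggers in 1.3.5 and 6.3.3 also use 4 weeks, for example "If 2 patients at a dose-level experience DLT events during the first 4 weeks of treatment".

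Three further provisions bear on the point. Section 6.3.3 convenes the DRC once the last patient in the cohort has completed 4 weeks, and adds that "the focus will be on observations from the first 4 weeks of treatment at that dose level". Section 1.3.5 says "The DRC review will include all safety data available for the cohort". Section 6.6.1 makes a patient evaluable for DRC review either by stopping treatment for a DLT as 6.3.1 defines it, or if the patient "Received all doses of study drug in the first 4 weeks of treatment and completed Week 5 assessment procedures".

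**The concern.** The definition and the count should cover the same days. Here a qualifying event in the fifth week meets the DLT definition, and 6.3.1 says that definition serves the MTD decision, yet the MTD rule does not count the event. It is not a DME either, because DMEs begin only after Week 5.

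The RP2D must be at or below the MTD (6.3.2), and up to 22 expansion patients are treated at the RP2D (6.4). Suppose a level has one DLT by Day 28 and a second on Days 29-35. If every 6.3.1 DLT counts, two patients have had DLTs and the level is above the MTD. If only the 4-week events in 6.3.2 count, one patient has, and the level is tolerated. Safety and tolerability is the primary objective, so the same data should not support both conclusions.

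**Working it through.** **The gap in days.** Section 9.1 sets Week 1 as Days 1-7. Four weeks are then Days 1-28 and five weeks Days 1-35, so the gap is Days 29-35.

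| Provision | Window or timing | DLT on Days 29-35 |
|---|---|---|
| 6.3.1, DLT definition | Days 1-35 | Is a DLT |
| 6.3.1, DME | Day 36 onward | Is not a DME |
| 6.3.2, both MTD criteria | Days 1-28 | Not counted |
| 1.3.5 and 6.3.3, triggers | Days 1-28 | Not counted |
| 6.3.3, DRC meeting | After last patient's 4 weeks | May not yet be observed |
| 6.6.1, evaluable by DLT | As in 6.3.1 | Makes a patient who stops treatment for it evaluable |
| 6.6.1, evaluable by completion | 4 weeks of dosing plus Week 5 procedures | Week 5 results needed |

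**What falls in the gap.** The schedule of assessments (1.9, footnote 14) places the full safety panel on Day 1 and at Weeks 1 and 5 of each cycle, with a focused panel at Weeks 3 and 7. In 9.7.1 the focused panel is the starred tests. Coagulation and the unstarred chemistry tests therefore have their first scheduled post-dose measurement at Week 5, nominally Day 29 before dosing. Section 10.4.2 (Table 13) dates a laboratory event by its sample. A confirmed, drug-related Grade 3 or higher result on that panel is a DLT under 6.3.1 and is outside the 6.3.2 count.

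**Size.** The protocol states no operating characteristic for the escalation rule, so there is no figure to reproduce. The following is an illustration on assumed rates.

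- Let p be the assumed 5-week DLT rate. With constant weekly hazard h = -ln(1-p)/5, the 4-week rate is q = 1 - exp(-4h).
- Under a strict 3+3 rule a level passes with 0 of 3 DLTs, or 1 of 3 followed by 0 of 3 more: P(pass) = (1-x)³ + 3x(1-x)⁵, with x = p for the 5-week count and x = q for the 4-week count.
- In a full cohort of six, each patient has a first DLT by Week 4 (probability q), in Week 5 only (p - q), or neither (1 - p). The verdicts are opposite when at most one patient has a DLT by Week 4 and at least two have one by Week 5.

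Worked case, p = 0.10: h = 0.0211 and q = 0.081. The 5-week count gives 0.729 + 0.177 = 0.906. The 4-week count gives 0.777 + 0.159 = 0.936.

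| 5-week rate p | 4-week rate q | P(pass), 5 weeks | P(pass), 4 weeks | Difference (points) | Opposite verdicts, 6 patients |
|---|---|---|---|---|---|
| 5% | 4.0% | 97.3% | 98.2% | 1 | 1.1% |
| 10% | 8.1% | 90.6% | 93.6% | 3 | 3.6% |
| 20% | 16.4% | 70.9% | 78.6% | 8 | 8.9% |
| 30% | 24.8% | 49.4% | 60.4% | 11 | 11.8% |
| 33% | 27.4% | 43.4% | 54.8% | 11 | 12.0% |

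**Cross-check from the other direction.** Take the assumed rate as the 4-week rate p4, so that p5 = 1 - (1 - p4)^(5/4). The chance of passing under the 4-week and 5-week counts is then 0.906 and 0.865 at p4 = 10%, 0.709 and 0.614 at 20%, 0.494 and 0.379 at 30%, and 0.309 and 0.205 at 40%. The difference is again about 4 to 12 points.

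**The case against.** The best defence is that the texts are nested. Only 6.3.2 sets a two-patient threshold, and it carries its own 4-week window. The references in 6.3.1 to escalation and the MTD point forward to the later sections. The 5-week definition would then serve wider purposes, such as managing individual patients, and the 4-week subset would serve counting. It is true that 6.3.1 has no threshold of its own. But the nested reading still drops Week 5 DLTs from a decision that 6.3.1 says its definition serves, and no sentence states that a subset is intended.

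A second defence is that the DRC sees everything. Because 6.6.1 requires Week 5 procedures, the committee should have the nominal Day 29 panel for each patient who is evaluable by completion. DLTs remain in scope for the RP2D, which rests on clinical data and which the sponsor may change during expansion (6.4). This stands as mitigation: a Week 5 DLT need not be ignored. It does not say whether that DLT counts toward the limit of two, and 6.3.3 still convenes the DRC at 4 weeks. The DRC Charter, which is not shown, may help in practice but cannot correct the protocol text.

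A third defence concerns size. Two DLTs trigger a pause and a DRC review, not an automatic stop, and a cohort may close at three patients, so the strict 3+3 and six-patient figures are simplifications. Section 4.4.1 mentions one DLT with 19 patients treated at up to 2.4 mg/kg/week, about 5% (1/19), which corresponds to the one-point row. That is fair as context. It is not a planning rate, however: the denominator printed for the 2.4 mg/kg level (88) cannot be right with 19 patients treated, and 3.6 mg/kg once weekly has still to be tested.

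**Conclusion.** The concern holds. The protocol uses two DLT windows for one decision, and Days 29-35 fall between them. The contradiction is in the text and does not depend on any assumed rate.

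Its size does depend on assumptions: constant hazard, a strict 3+3 rule without DRC discretion and, for the opposite-verdict figures, a full cohort of six. On those terms it is about one point on the chance of passing a level at a 5-week DLT rate of 5%, and about 11 points at 30-33%. The effect would be larger if DLTs cluster at the Week 5 visit, which is plausible for tests first repeated there. Because the MTD caps the expansion dose, this should be corrected and not left to the DRC to interpret.

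**What to change.** Use one DLT window in 1.3.5, 6.3.1, 6.3.2, 6.3.3 and 6.6.1. Either of two would work:

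- **Option A:** Day 1 through completion of the Week 5 pre-dose assessments. This fits the existing evaluability rule in 6.6.1.
- **Option B:** Day 1 through Day 35. This matches 6.3.1 and requires 6.6.1 to be extended to Day 35.

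Under either option:

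- State that Week 5 pre-dose results count toward the DLT tally.
- Convene the DRC only when the last patient's Week 5 results (A) or Day 35 data (B) are available.
- Start the DME period immediately after the window closes, so that no day is left unclassified.

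The cost is wording in five sections, and in the DRC Charter if it repeats the window, plus at most about one extra week per cohort review.
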